7.6.4. Exploratory Analyses

7.6.4.1. FFI Composite Score

The mean change from Baseline (Day 1) to Days 15, 29, 43, and 57 on FFI total composite score with EN3835 vs placebo and their treatment differences will be estimated using the similar statistical model based on observed data using MMRM (Section 7.6.1.3).

The LSM estimate for the mean change from baseline on FFI total composite score at each visit for each treatment group and the LSM for treatment difference at each visit and their 95% confidence interval (CI) will be presented.

The descriptive statistics for observed and change from baseline on the composite score on FFI by visit and treatment group will be provided.

A listing of the FFI total score (derived) by participant will be provided.

7.6.4.2. Patient Global Impression of Severity

A listing will be provided for PGIS PF Overall scores, PGIS foot pain subscale scores, PGIS difficulty subscale scores and PGIS activity limitation subscale scores by participant.

7.6.4.2.1. Difference between EN3835 and Placebo at Day 15, 29, 43 and 57 in the PGIS PF Overall Score

The differences in the PGIS PF Overall scores at Day 15, 29, 43 and 57 between EN3835 and placebo will be tested using the Wilcoxon rank-sum test; corresponding p-values will be provided. In addition, the median difference/location shift between the treatment groups at each visit and corresponding 95% CIs using the Hodges-Lehmann estimator will be provided.

PGIS PF overall scores will be summarized using frequency and percentages of participant with mean and SD by treatment group and visits.

7.6.4.2.2. Difference between EN3835 and Placebo at Day 15, 29, 43 and 57 on the PGIS Foot Pain Subscale Score.

The change in PGIS foot pain subscale scores at Day 15, 29, 43 and 57 between EN3835 and Placebo will be tested using the Wilcoxon rank-sum test and the p-value will be provided. In addition, the Hodges-Lehmann estimator and its 95% CIs will be provided to represent the median difference/location shift between the treatment groups at each visit.

PGIS foot pain subscale scores will be summarized using frequency and percentages of participant with mean and SD by treatment group and visits.

7.6.4.2.3. Difference between EN3835 and Placebo at Day 15, 29, 43 and 57 on the PGIS Difficulty Subscale Score.

The change in PGIS difficulty subscale scores at Day 15, 29, 43 and 57 between EN3835 and Placebo will be tested using the Wilcoxon rank-sum test and the p-value will be provided. In addition, the Hodges-Lehmann estimator and its 95% CIs will be provided to represent the median difference/location shift between the treatment groups at each visit.

PGIS difficulty subscale scores will be summarized using frequency and percentages of participant with mean and SD by treatment group and visits.

7.6.4.2.4. Difference between EN3835 and Placebo at Day 15, 29, 43 and 57 on the PGIS Activity Limitation subscale score.

The change in PGIS activity limitation subscale score at Day 15, 29, 43 and 57 between EN3835 and Placebo will be tested using the Wilcoxon rank-sum test and the p-value will be provided. In addition, the Hodges-Lehmann estimator and its 95% CIs will be provided to represent the median difference/location shift between the treatment groups at each visit.

PGIS activity limitation subscale scores will be summarized using frequency and percentages of participant with mean and SD by treatment group and visits.

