
 To assess the safety and tolerability of EN3835 in participants with plantar fibromatosis. 	
 Safety of EN3835 as assessed by incidence, severity and duration of treatment-emergent adverse events (TEAEs), adverse events of special interest (AESIs), and serious adverse events (SAEs). The change from baseline in vital signs and clinical laboratory values at each visit where these parameters are measured.

 To assess the immunogenicity of EN3835 in participants with plantar fibromatosis. 	
 Presence of anti-AUX-I and anti-AUX-II antibody titer levels in EN3835 treated-participants at Day 1 and Day 57. Presence of neutralizing antibodies to AUX-I and AUX-II in EN3835 treated-participants at Day 1 and Day 57.
Exploratory	

 To assess the overall improvement in the FFI composite score with EN3835 vs placebo. 	
 The difference between EN3835 and placebo in the mean change from Baseline (Day 1) to Day 57 on the FFI composite score, with the score of each of the 21 items ranging from 0 to 4, with 4 indicating higher severity. The mean change from Baseline (Day 1) to Days 15, 29, 43, and 57 on the FFI composite score with EN3835 vs placebo.

 To assess the overall improvement in severity of plantar fibromatosis on the Patient Global Impression of Severity (PGIS) PF Overall scale. 	
 The difference between EN3835 and placebo at Day 57 on the PGIS PF Overall score. The difference between EN3835 and placebo Days 15, 29, 43, and 57 on the PGIS PF Overall score with EN3835 vs placebo.

 To assess the overall improvement in the severity of foot pain with EN3835 vs placebo in the PGIS foot pain subscale. 	
 The difference between EN3835 and placebo at Day 57 on the foot pain subscale of the PGIS. The difference between EN3835 and placebo at Days 15, 29, 43, and 57 on the PGIS foot pain subscale, ranging from 0 ("None") to 4 ("Severe") with EN3835 vs placebo.

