10.3.1.2.4. Other Secondary Endpoints and Exploratory Endpoints

The other secondary endpoints and exploratory endpoints including the mean changes from Baseline (Day 1) to study visits (Days 15, 29, 43 and 57) for FFI- Pain and Difficulty combined score, FFI- pain subscale, FFI- difficulty subscale, and FFI-activity limitation subscale, FFI-composite score, Pain intensity NRS, nodule size, and hardness measurement will be analyzed using the MMRM method based on observed data. The LSM estimates for the treatment difference at each visit and their corresponding 95% CIs will be reported.

The PGIS (overall, pain, difficulty, and activity limitation subscales) scores at each study visit (Days 15, 29, 43, and 57) will be compared between treatment groups using a rank based

analysis. The Hodges-Lehmann estimator and its 95% CIs will be provided to represent the median difference/location shift between the treatment groups.

In addition, response rates for the PGIC for PF overall and each individual subscale, participant satisfaction with treatments, Clinician Global Impression of Change Scale, and nodule consistency will be compared between treatment groups using the Cochran-Mantel-Haenszel method. The responder definition for each assessment will be detailed in the SAP.

Psychometric properties of the FFI will be assessed under a separate SAP. A series of tests are proposed to validate the FFI in the plantar fibromatosis patient population. Upon completion of the analyses, an overall impression and conclusion regarding the psychometric properties of the FFI instrument will be made, based on the analysis results.

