7.6.4.3.1. Patient Global Impression of Change - PF Overall Score

The difference in proportion of responders between EN3835 and placebo will be analyzed using CMH test stratified by baseline severity score (ie, PGIS-PF Overall) separately for each visit.

The stratum adjusted risk difference (RR) from the CMH test, associated 95% CI and p-value will be presented separately for each visit. The frequency and percentage of responders (Section 4.7.3.1) and 95% CI will be provided based on the Wilson (Score) by treatment group and visit.

The degree of improvement in the 7-point scale as determined by the investigator using PGIC – PF overall will be summarized using frequency and percentages with mean and SD by each treatment group and visit.

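### The exploratory PGIS tests leave out the Day 1 PGIS score that the trial collects, and three of the four PGIS subsections say *change* where the endpoint is the score at the visit

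*SAP*

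**What the plan says.** **Endpoint.** Protocol Section 4 defines the PGIS endpoints as scores at a visit, for example "The difference between EN3835 and placebo at Day 57 on the PGIS PF Overall score". Protocol 10.3.1.2.4 repeats this: PGIS "scores at each study visit (Days 15, 29, 43, and 57) will be compared between treatment groups using a rank based" analysis, with a Hodges-Lehmann estimate and 95% CI.

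**Test.** For PF Overall, SAP 7.6.4.2.1 says that differences in scores "between EN3835 and placebo will be tested using the Wilcoxon rank-sum test; corresponding p-values will be provided". SAP Table 27 lists the Wilcoxon test and Hodges-Lehmann estimator, in the mITT population, for all four PGIS scales. None of these places names a baseline stratum or covariate.

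**Subscales.** SAP 7.6.4.2.2 reads "The change in PGIS foot pain subscale scores at Day 15, 29, 43 and 57 between EN3835 and Placebo will be tested". SAP 7.6.4.2.4 reads "The change in PGIS activity limitation subscale score at Day 15, 29, 43 and 57 between EN3835 and Placebo will be tested". SAP 7.6.4.2.3 (difficulty) follows the same pattern.

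**Baseline PGIS elsewhere.** The Schedule of Assessments has all PGIS scales at Screening and Day 1. SAP 7.6.4.3.1 analyses PGIC PF Overall with a "CMH test stratified by baseline severity score (ie, PGIS-PF Overall) separately for each visit". The three PGIC subscales are stratified by their matching PGIS scores, and satisfaction by PGIS PF Overall (SAP 7.6.4.5).

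**The concern.** There are two issues.

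1. **Precision.** The baseline value of the same instrument is available and already serves as a stratifier for two other scales. Leaving it out of the PGIS comparison means that a chance imbalance in baseline severity stays in the estimate, and any precision that baseline could supply is lost. The SAP gives no reason.
2. **Variable.** SAP Table 25 defines change from baseline as the post-baseline value minus the baseline value. A programmer who applies that definition to the three subscale sentences would test a different quantity from the one tested for PF Overall, and from the one in the protocol. SAP Table 28 records no such departure. The choice can also alter the result, as the working shows.

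**Working it through.** **The plan's own figure.** Protocol 10.1 gives a difference of 5.0, SD 10, 85% power and two-sided alpha 0.05, for FFI pain only.

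- Normal approximation: n per arm = 2 × (1.960 + 1.036)² × (10/5)² = 71.8, so 72. The two-sample t-test gives 72.8, so 73, as stated.
- Dropout: 146 / (1 − 0.15) = 171.8, so 172, as stated.

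The documents state no effect size, correlation or power for PGIS. Everything below rests on assumptions, with 73 per arm borrowed from the primary endpoint.

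**Normal-theory guide.** With correlation ρ between baseline and follow-up, the SD is multiplied by √(1 − ρ²) for a baseline-adjusted comparison and by √(2(1 − ρ)) for a change score. With a 0.5 SD effect, the unadjusted power is 86%.

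| ρ | Effective sample size, 1/(1 − ρ²) | Power, adjusted | Power, change score |
|---|---|---|---|
| 0.3 | 1/0.91 = 1.10 | 89% | 72% |
| 0.5 | 1/0.75 = 1.33 | 94% | 86% |
| 0.7 | 1/0.51 = 1.96 | 99% | 97% |

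**Simulation on a 5-level scale.** Scores were cut from an underlying bivariate normal, with 73 per arm. Rows with a 0.5 SD shift use 4,000 runs per setting (Monte Carlo SE about 0.6 points) and a baseline mostly at Moderate or Severe; the observed rank correlation is in brackets. Rows with a 0.45 SD shift come from a separate run. Correlations are those of the underlying normal variables.

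| Correlation | Shift (SD) | Wilcoxon on scores | van Elteren by baseline | Gain (points) |
|---|---|---|---|---|
| 0 | 0.45 | 71% | 70% | −1 |
| 0 (0.00) | 0.5 | 81.7% | 80.5% | −1.2 |
| 0.2 | 0.45 | 73% | 73% | 0 |
| 0.3 (0.25) | 0.5 | 81.3% | 82.5% | 1.2 |
| 0.4 | 0.45 | 73% | 77% | 4 |
| 0.5 (0.42) | 0.5 | 80.7% | 87.4% | 6.7 |
| 0.6 | 0.45 | 73% | 85% | 12 |
| 0.7 (0.59) | 0.5 | 80.7% | 94.5% | 13.8 |

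Rank ANCOVA gives similar figures; at observed correlation 0.25 its gain is 83.8 − 81.3 = 2.5 points. A wider baseline distribution changes little; at observed correlation 0.62 the gain is 95.2 − 80.4 = 14.8 points. With no treatment effect, rejection rates in the 4,000-run simulation were 4.3% to 5.6% for every method.

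**Score against change.** With the 0.5 SD shift and the mostly Moderate/Severe baseline, a Wilcoxon test on change has 65%, 78%, 86% and 94% power at observed correlations of about 0, 0.25, 0.42 and 0.6. The test on scores stays near 81%. With the wider baseline, the change figures are 54%, 67%, 79% and 93%. The two readings are not interchangeable, and which is more powerful depends on the correlation.

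**The case against.** The case for leaving the test alone is substantial.

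- **It follows the protocol.** The protocol asks for a rank-based comparison of scores with a Hodges-Lehmann estimate, and the SAP supplies one. The amendment history shows that the move from mean change to scores was deliberate.
- **It is valid.** Randomization protects the unadjusted Wilcoxon test, and the simulated type I error agrees. A reader might infer that chance baseline imbalance makes the result biased or the test wrong. The documents and the calculation do not support that; the loss is precision only.
- **The comparators are imperfect.** PGIC and satisfaction have no Day 1 value of their own, so stratifying them by PGIS sets no rule for PGIS. CGIC, a key secondary endpoint, is stratified by number of nodules. It would be too much to say that every other scale is adjusted for its own baseline.
- ***Change* may be loose wording.** The sentences never add *from baseline*, and the headings above them describe a difference in scores. It is therefore not established that the four scales would be analysed differently.

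All of this limits the point, but two things remain. The protocol's wording leaves room for a stratified rank test that uses data already in hand. The subscale sentences do conflict with their headings, and the conflict should not be left to the programmer.

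**Conclusion.** The point holds as one of efficiency and clarity. The wording conflict needs correcting in any case; baseline stratification is a recommended improvement.

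The gain is nil at correlation 0, about 0 to 3 points at 0.2 to 0.25, 4 to 7 near 0.4 and 12 to 14 near 0.6. These figures assume 73 per arm and a 0.45 to 0.5 SD shift. The FFI pain entry floor of 50% (Protocol 6.1, criterion 3) may narrow baseline PGIS and shrink the gain.

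Three stronger readings go too far:

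- That baseline is ignored on all four scales. This is secure only for PF Overall; if *change* is meant literally, the other three do use baseline.
- That PGIS serves as the global anchor for the FFI pain result. Neither document gives it that role, and FFI psychometrics fall under a separate SAP.
- That the trial's conclusions are at risk. PGIS is exploratory, outside the testing hierarchy and reported with nominal p-values (SAP 6.5).

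**What to change.** 1. In SAP 7.6.4.2.2 to 7.6.4.2.4, replace *change* with *score* at the visit, to match the headings, Tables 1 and 27 and the protocol.
2. For all four scales, test the score at each visit with a van Elteren test stratified by the Day 1 score of the same PGIS scale, with baseline as defined in SAP Table 25. State in advance how sparse levels are pooled; the adjacent-group rule for subgroups of fewer than 10 in SAP 7.6.5 is a ready model.
3. Report a stratified Hodges-Lehmann shift with its 95% CI, and state how it is computed.
4. Amend the four PGIS rows of Table 27 to match.

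A proportional-odds model is not recommended as an alternative: it yields an odds ratio, not the location shift that Protocol 10.3.1.2.4 promises.

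The cost is a few lines of SAP text and some programming, with no new data. The method stays rank based, so a protocol amendment does not appear necessary. The change should be made before database lock, by when Protocol 10.3 requires the SAP to be final; settling the variable or the strata after unblinding would look data-driven.

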7.6.4.3. Patient Global Impression of Change

A listing will be provided for PGIC PF Overall scores, PGIC foot pain subscale scores, PGIC difficulty subscale scores and PGIC activity limitation subscale scores by participant.

7.6.4.3.1. Patient Global Impression of Change - PF Overall Score

The difference in proportion of responders between EN3835 and placebo will be analyzed using CMH test stratified by baseline severity score (ie, PGIS-PF Overall) separately for each visit.

The stratum adjusted risk difference (RR) from the CMH test, associated 95% CI and p-value will be presented separately for each visit. The frequency and percentage of responders (Section 4.7.3.1) and 95% CI will be provided based on the Wilson (Score) by treatment group and visit.

The degree of improvement in the 7-point scale as determined by the investigator using PGIC – PF overall will be summarized using frequency and percentages with mean and SD by each treatment group and visit.

7.6.4.3.2. Patient Global Impression of Change - Foot Pain Subscale Score

The difference in proportion of responders between EN3835 and placebo will be analyzed using CMH test stratified by baseline severity score (ie, PGIS – Foot Pain Subscale Score) separately for each visit.

The stratum adjusted risk difference, associated 95% CI and p-value will be presented separately for each visit. The frequency and percentage of responders (Section 4.7.3.2) and 95% CI will be provided based on the Wilson (Score) by treatment group and visit (ie, Days 15, 29, 43, and 57).

The degree of improvement in the 7-point scale as determined by the investigator using PGIC – Foot Pain Subscale will be summarized using frequency and percentages with mean and SD by each treatment group and visit.

7.6.4.3.3. Patient Global Impression of Change - Difficulty Subscale Score

The difference in proportion of responders between EN3835 and placebo will be analyzed using CMH test stratified by baseline severity score (ie, PGIS – Difficulty Subscale Score) separately for each visit.

The risk difference, associated 95% CI and p-value will be presented separately for each visit. The frequency and percentage of responders (Section 4.7.3.3) and 95% CI will be provided based on the Wilson (Score) by treatment group and visit.

The degree of improvement in the 7-point scale as determined by the investigator using PGIC – Difficulty Subscale will be summarized using frequency and percentages with mean and SD by each treatment group and visit.

7.6.4.3.4. Patient Global Impression of Change - Activity Limitation Subscale Score

The difference in proportion of responders between EN3835 and placebo will be analyzed using CMH test stratified by baseline severity score (ie, PGIS – Activity Limitation Subscale Score) separately for each visit.

The stratum adjusted risk difference, associated 95% CI and p-value will also be presented separately for each visit. The frequency and percentage of responders (Section 4.7.3.4) and 95% CI will be provided based on the Wilson (Score) by treatment group and visit.

The degree of improvement in the 7-point scale as determined by the investigator using PGIC – Activity Limitation Subscale will be summarized using frequency and percentages with mean and SD by each treatment group and visit.

7.6.4.4. Pain Intensity Numerical Rating Scale

7.6.4.4.1. Mean Change from Baseline to Day 15, 29, 43 and 57 on the Pain Intensity NRS

The mean change from Baseline (Day 1) to Days 15, 29, 43, and 57 in Pain Intensity NRS with EN3835 vs placebo and their treatment differences will be estimated using the similar statistical model based on observed data using MMRM (Section 7.6.1.3).

The LSM estimate for the mean change from baseline at each visit for each treatment group and the LSM for treatment difference at each visit and their 95% confidence interval (CI) will be presented.

The descriptive statistics for observed and change from baseline on the Pain Intensity NRS by visit and treatment group will be provided.

A listing for Pain Intensity NRS will be provided by participant.

7.6.4.5. Subject Satisfaction with Treatment Scale

The difference in proportion of responders between EN3835 and placebo will be analyzed using CMH test stratified by baseline severity score (ie, PGIS – PF Overall Score) separately for each visit.

The stratum adjusted risk difference, associated 95% CI and p-value will also be presented separately for each visit. The frequency and percentage of responders (Section 4.7.5) and 95% CI will be provided based on the Wilson (Score) by treatment group and visit (ie, Days 15, 29, 43, and 57).

The degree of improvement in the 5-point scale as determined by the investigator using Subject Satisfaction with Treatment Scale will be summarized using frequency and percentages with Mean and SD by each treatment group and visit (ie, Days 15, 29, 43, and 57) for each foot.

A listing of Subject Satisfaction with Treatment Scale will be provided by participant.

7.6.4.6. FFI Individual Subscales Scores

7.6.4.6.1. Mean Change from Baseline to Days 15, 29, 43 and 57 on the FFI- Activity Limitation Subscale

The mean change from Baseline (Day 1) to Days 15, 29, 43, and 57 on the FFI-Activity Limitation Subscale for EN3835 vs placebo and their treatment differences will be estimated using the similar statistical model based on observed data using MMRM (Section 7.6.1.3).

The LSM estimate for the mean change from baseline at each visit for each treatment group and the LSM for treatment difference at each visit and the corresponding 95% CI will be presented.

The descriptive statistics for observed and change from baseline on the activity limitation subscale by visit and treatment group will be provided.

The listing of FFI will include the activity limitation score by participant.

7.6.4.6.2. Mean Change from Baseline to Days 15, 29, 43 and 57 on the FFI - Difficulty Subscale Score

The mean change from Baseline (Day 1) to Days 15, 29, 43, and 57 on the difficulty subscale (total score on 9 items) of the FFI, ranging from 0 (“No Difficulty”) to 4 (“A Lot of Difficulty”) with EN3835 vs placebo and their treatment differences will be estimated using the similar statistical model based on observed data using MMRM (Section 7.6.1.3).

The LSM estimate for the mean change from baseline at each visit for each treatment group and the LSM for treatment difference at each visit and their 95% confidence interval (CI) will be presented.

The descriptive statistics for observed and change from baseline at each visit on the difficulty subscale score by treatment group will be provided.

The listing of FFI will include the difficulty subscale score by participant.

7.6.4.7. Nodule Size by Caliper Measurement

7.6.4.7.1. Participant Level Analyses: Mean change from Baseline to Days 15, 29, 43 and 57 in the size of the treated nodules

The mean change from Baseline (Day 1) to Days 15, 29, 43, and 57 in the size of the treated nodules with EN3835 vs placebo and their treatment differences will be estimated using the similar statistical model based on observed data using MMRM (Section 7.6.1.3).

The LSM estimate for the mean change from baseline at each visit for each treatment group and the LSM for treatment difference at each visit and their 95% confidence interval (CI) will be presented.

The descriptive statistics for observed and change from baseline at each visit by treatment group will be provided. The nodule size (up to 2 cm, > 2 cm to ≤4 cm and > 4 cm) will also be summarized by each treated nodule.

A listing for nodule size will be provided by participant.

7.6.4.7.2. Nodule Level Analyses: Mean change from Baseline to Days 15, 29, 43 and 57 in the size of the treated nodules

Nodule level analyses will be performed on observed data using MMRM (Section 7.6.1.3).

The mean change in nodule size from baseline to Days 15, 29, 43, and 57 in EN3835 compared to placebo will be analyzed using a MMRM. An unstructured covariance matrix will be used to model the covariance of within-participant values. The Kenward-Roger approximation will be used to estimate denominator degrees of freedom. If the convergent criteria are not met then

other covariance matrix structure, ie., autoregressive (1) (AR (1)) will be used for model. The MMRM model will include:

- The dependent variable, the change from the Baseline to each visit (ie, change from baseline score to day 15, day 29, day 43, and day 57)
- The fixed effect, treatment group, study visit, treatment by visit interaction.
- The covariate, the baseline maximum of Nodule length/Nodule width for respective nodule at Day 1, maximum of Nodule length/Nodule width for respective nodule.
- The repeated measures will be the study visit and nodules.

The least square mean (LSM) estimate for each treatment at EOS, the LSM of treatment difference, their corresponding 95% confidence interval (CI) and associated p-value will be provided.

